1.0 Study Summary

Study Title	Episodic Thinking and Alcohol Use
Study Design	Participants will be enrolled in the study, complete two sessions and undergo a one week baseline monitoring phase where they provide breath samples to assess for recent alcohol use and report their drinks per day. Following this baseline period, participants will complete an fMRI and then be randomized to either the EFT or Control group. Participants will then complete two weeks of monitoring, where they provide a breath sample three times a day and report the number of drinks they consumed. Participants will then come back to the lab to generate new EFT/CET cues, then complete two more weeks of monitoring. After conclusion of the second intervention period, participants will complete a post intervention session, including an fMRI, and then a one month follow up one month after study completion.
Primary Objective	The primary outcome measures of this study are the extent to which EFT increases an individual's temporal window and decreases their alcohol valuation, compared to baseline and/or the CET condition.
Secondary Objective(s)	N/A
Study Population	Individuals with Alcohol Use Disorder
Sample Size	200
Research Intervention(s)/ Investigational Agent(s)	In the EFT intervention, participants will generate positive future events they are looking forward to at 7 time points in the future (1 day, 1 week, 1 month, 3 months, 1 year, 5 years, and 25 years). Participants will be reminded of these events using cues throughout the study and instructed to think about these cues as they make their decisions. In contrast, in the CET intervention, participants will generate positive recent past events that have happened to them at 7 time points from the recent past (last night from 7pm-10pm, yesterday between 4pm-7pm, yesterday between 1pm-4pm, yesterday from 10am-12pm, yesterday between 7am-10am, the night before last between 7pm-10pm, and evening before last between 4pm-7pm). Participants will be reminded of these events using cues throughout the study and instructed to think about these cues as they make their decisions.
Study Duration for Individual Participants	The total study is expected to take up to approximately 15 weeks.
Acronyms and Definitions	AUD = Alcohol Use Disorder

	CET = Control Episodic Thinking
	EFT = Episodic Future Thinking

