4.0 Study Endpoints

*4.1 Describe the primary and secondary **study** endpoints. See links below for discussion of study endpoints and how they may differ from study objectives. These are most common in clinical trials but are sometimes applicable to other types of biomedical research, as well as social, behavioral, or educational research. See link below for a discussion.*

https://docs.google.com/document/d/1Wocz7K7a0hCQJPPO_khh511SQjhGDDGHzcOPRHR5Tw/edit?usp=sharing

Delay discounting: Change in discounting rates will be compared within-subjects between pre intervention and post intervention. In addition, differences in discount rates will be compared between groups (EFT and CET).

Alcoholic Drinks: Change in drinks per day and number of positive breath alcohol samples (BrAC) will be compared within-subjects between pre intervention and post intervention. In addition, differences in drinks per day and number of positive BrAC samples will be compared between groups (EFT and CET).

Alcohol Demand: Change in demand for alcohol will be compared within-subjects between pre intervention and post intervention. In addition, differences in alcohol demand will be compared between groups (EFT and CET).

Alcohol Craving: Change in alcohol craving will be compared within-subjects between pre intervention and post intervention. In addition, differences in alcohol craving will be compared between groups (EFT and CET).

4.2 *Describe any primary or secondary safety endpoints. These should be included for all studies that are greater than minimal risk. (Minimal risk: The probability and magnitude of harm or discomfort anticipated in the research that are not greater in and of themselves than those ordinarily encountered in daily life or during the performance of routine physical or psychological examinations or tests.):*

This study's procedures are not more than minimal risk.

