Primary hypotheses: Our primary measure of temporal window is delay discounting (DD). Our primary measure of alcohol consumption is self-reported drinks per day. Participants are asked to report how many standard drinks they had for the previous 24 hours on each day of the 7 day baseline and 28 day intervention period. Our secondary measure of alcohol consumption is breath alcohol samples from the remote breathalyzer. Participants will provide three breath samples daily for the 7 day baseline and 28 day intervention period. Our primary measures of demand are alpha and Q0. Alpha and Q0 are two derived outcomes from a hypothetical alcohol purchase task. Participants are asked to report the number of standard drinks they might hypothetically purchase at increasing price points. Q0 is a measure of how many drinks a participant might purchase when drinks are free (price = \$0). Alpha is a measure of the participants sensitivity to increasing prices (i.e., how quickly they decide to stop purchasing at higher prices). Our measure of craving is the Alcohol Urges Questionnaire (AUQ). Our measure of neural activity is BOLD response. We hypothesize that baseline BOLD response will be predictive of the efficacy of the intervention. We will model our primary outcome measures using a mixed-effects hierarchical model that includes day, time (pre/post intervention), and intervention group. A random effect will be included for each participant. We will include baseline BOLD response as a fixed-effect covariate in our analysis.

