Following informed consent (Session 1), participants will complete a second session (Session 2). Sessions 1 and 2 may be on the same day. Following this session, participants will be asked to provide daily self-report assessments of previous-day drinking remotely (see below) and 3 breathalyzer samples per day for 7 days with no other study intervention taking place and their alcohol withdrawal symptoms per day. The purpose for this baseline period is to quantify baseline drinking patterns and ensure that the participant reliably responds to and conveys study information remotely. At the end of this baseline period, participants who indicated adequate patterns of drinking on at least 4 of the 7 days and successfully reported their level of drinking as requested on 5 of the 7 baseline days will be invited to continue in the study.

Following the baseline period, participants will return to the laboratory for Session 3. During Session 3, participants will complete an fMRI. Participants will be

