14.0 Number of Subjects

14.1 Indicate the total number of subjects to be enrolled and how this number was determined (e.g., sample size calculation [show], number of available subjects in a finite pool, number of tests funding award would allow):

Although we have observed large effect sizes of EFT on DD in AUD participants in our preliminary studies (pre-post $d=1.6$; post-only $d = 0.68$), we used a more conservative medium effect size ($f= 0.25$) to inform sample sizes to increase power to detect effect on the broader range of measures proposed here (e.g., intensity of demand). Using the method proposed by Borm, Fransen, and Lemmens, and a pre- and post-measurement correlation of 0.70218, 76 total participants would be needed to complete this study (38 participants per group), assuming a type 1 error rate of 0.01 and 95% statistical power, based on an ANCOVA comparing the intervention while using the baseline measure as a fixed-effect covariate in the analysis.

We have been successfully recruiting individuals with AUD in our community for the past 8 years. Based on these 8 years of experience recruiting alcohol users into studies of comparable length and complexity, we anticipate that over 80% of consented participants will be eligible (i.e., randomized) and about 65% of those eligible individuals will complete this study. Thus, to achieve a final sample size of 76, we anticipate consenting 200 participants. We plan to enroll more than our average attrition rate because of the increased procedures and the time demands of the study.

14.2 If this is a multi-site study, indicate the number of subjects to be enrolled at this site and the total to be enrolled from all sites:

N/A

14.3 If applicable, indicate the number of potential subjects you expect to screen for enrollment, and the number of subjects you will need to complete the research procedures:

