Exclusion criteria include: (1) meeting moderate to severe DSM-5 criteria for substance-use disorders other than alcohol, nicotine, or marijuana, (2) having a current diagnosis of any psychotic disorder, (3) having a history of seizure disorders or traumatic brain injury, (4) having any contraindication for participation in the fMRI session, or (5) reporting current pregnancy or lactation.

Recruitment

Participants will be recruited from the community via posted flyers, word of mouth referrals, and electronic advertisements (e.g., Craigslist, Facebook). Participants may contact the lab directly via email, Facebook, phone, walk-in, face-to-face at tabling events, or completing the online pre-screening questionnaire. Participants will also be contacted directly if they have given prior permission (through previous informed consent form) or by completion of a confidential pre-screening questionnaire.

We have developed and are currently using a separate pre-screening protocol, which occurs prior to enrolling participants into our intervention protocols, to effectively decrease attrition in our studies by ensuring that participants meet most inclusion/exclusion criteria (e.g., MRI scanner eligibility) prior to enrolling into the randomized study. Given that this separate screening protocol is used for all currently on-going studies in the lab, we cannot accurately estimate the total number of potential participants we expect to screen. However, as described above, we expect enrolling 170 participants to complete 54. We plan to enroll more than our average attrition rate because of the increased screening procedures and the time demands of the study. Additionally, the first few participants enrolled into the study may be pilots.

Participant Retention

We will evaluate continuation in our study after a baseline period of drinking has been completed. We expect to retain 75% of our participants at this time point. Specifically, 75% of our participants will present with at least 4 out of 7 drinking days, and at least 4 days with 4 or more drinks or an average higher than 4 drinks per day on drinking days.

Once participants reach this study phase , we expect a 70% retention for the rest of the study.

Randomization

Participants will be randomly assigned to experimental or control groups, balanced by number of drinks per day (square root transformed) and baseline DD rates.

Sample size

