We will use a 3T Siemens MAGNETOM Prisma^{fit} scanner (Siemens, Erlangen, Germany) with a 20-channel head/neck coil. T1-weighted images will be acquired at $1 \times 1 \times 1 \text{ mm}^3$ resolution using 3D MPRAGE, FOV = $256 \times 256 \times 176 \text{ mm}^3$, TR/TE/TI = 1950/4.44/950 ms, FA = 12° , phase partial Fourier 7/8, slice partial Fourier 6/8, GRAPPA factor = 4 with 33 reference lines, and bandwidth = 140 Hz/pixel. Functional BOLD data will be acquired using EPI with thirty-three 4 mm interleaved slices with a 10% slice gap, TR/TE = 2000/30 ms, FA = 10° , in-plane resolution of $3.4 \times 3.4 \text{ mm}^2$, anterior-to-posterior phase encoding and a bandwidth = 2442 Hz/pixel. Participants will be instructed to keep their eyes open during the scan and direct their gaze on a white plus (+) sign centered on a black background.

Alcohol Consumption

Changes in drinks per day and the number of positive breath alcohol samples (BrAC) will be compared within subjects between pre-intervention and post-intervention. In

addition, differences in drinks per day and the number of positive BrAC samples will be compared between groups (EFT and CET). A Timeline Follow Back (TLFB⁴⁰) will be conducted during Session 2 (pre-intervention) and Session 6 (1-month follow-up) to assess the number of alcoholic drinks consumed daily for the past 30 days. During the intervention period (from Session 2 to Session 5), participants will report daily the number of alcoholic drinks consumed.

Alcohol Urges Questionnaire (AUQ)

The Alcohol Urges Questionnaire ⁴¹ will be used to assess craving for alcohol. This 8-question measure of drinking urges is scored by summing responses to a 7-point Likert scale. The dependent measure of the summed score will be compared within subjects between pre-intervention and post-intervention. In addition, differences in alcohol craving will be compared between groups (EFT and CET).

Alcohol Use Disorders Identification Test (AUDIT)

The Alcohol Use Disorders Identification Test (AUDIT⁴²) will be used to assess hazardous or harmful alcohol use. AUDIT is a 10-item screening tool that assesses alcohol consumption, drinking behaviors, and alcohol-related problems. Differences in alcohol AUDIT scores will be compared between groups (EFT and CET).

Alcohol Relative Reinforcement Schedule (ARRS)

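### The primary objective admits a change from baseline with no control; for drinks per day and BrAC that comparison carries regression to the mean, so the primary conclusion should rest on EFT versus CET alone

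*Protocol*

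**What the plan says.** **Objective.** Protocol 1.0, Primary Objective, describes the primary outcome as the extent to which EFT lengthens the temporal window and lowers alcohol valuation, "compared to baseline and/or the CET condition".

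**Endpoints.** For each endpoint, Protocol 4.1 gives a pre/post comparison first and then adds EFT versus CET. For drinking: "Change in drinks per day and number of positive breath alcohol samples (BrAC) will be compared within-subjects between pre intervention and post intervention". The SAP repeats this under Alcohol Consumption ("Changes in drinks per day and the number of positive breath alcohol samples (BrAC) will be compared within subjects between pre-intervention and post-intervention") and plans the same for the AUQ. Neither document says that these comparisons are descriptive, or that EFT versus CET takes precedence.

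**Selection on the baseline week.** Under Protocol 8.2, those invited to continue are "participants who indicated adequate patterns of drinking on at least 4 of the 7 days", provided they also reported on 5 of the 7 days. The SAP (Participant Retention) supplies the amount: at least 4 drinking days of 7, and "at least 4 days with 4 or more drinks or an average higher than 4 drinks per day on drinking days". It adds: "We expect to retain 75% of our participants at this time point".

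**Same week as comparator.** Under Protocol 5.2, drinks per day is reported "on each day of the 7 day baseline and 28 day intervention period". The week used for selection is therefore also the pre-intervention value.

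**The concern.** A comparison with the arm's own baseline cannot separate EFT from anything else that changes over the same weeks. CET is in the trial to absorb such changes, and the *or* in the objective lets a claim bypass it.

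For drinking there is a specific and predictable bias. Participants are kept because a short, noisy measurement was high, and that same measurement is then the value from which change is counted. Their later mean will be lower on average with no treatment effect. If EFT and CET did equally well, both arms would tend to fall, and the objective as worded could still be reported as met.

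**Working it through.** The plan gives no figure for the pre/post comparison, so there is none to reproduce. The check has two parts.

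**1. Which comparison governs?**
- *Pointing to CET:* the hypothesis in Protocol 3.3 and the SAP Introduction; the SAP Objective 1 model for daily drinks; the SAP text on ln(k) and demand; the Protocol 14.1 sizing (ANCOVA); and the SAP sizing (group-by-time interaction).
- *Leaving it open:* the Primary Objective; Protocol 4.1; the SAP text on consumption and AUQ; and Protocol 2.2, which names no comparator. The Protocol 5.2 model lists day, time and group but does not name the deciding contrast.
- No text ranks one set above the other.

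**2. How large is regression to the mean for drinks per day?**

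*Inputs from the documents:* fraction kept k = 0.75 (SAP); 38 per arm (Protocol 14.1) or 26 per arm (SAP); 7 baseline and 28 intervention days; analysis level 0.05 (SAP).

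*Assumptions:* normal scores; selection on the observed baseline score; no treatment effect; reliability R of the 7-day mean of 0.5, 0.7 or 0.9. The documents give pre/post correlations of 0.70218 and 0.5, but neither is stated to be for drinks.

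Baseline SD before selection is set to 1.
- Cut-off: c = −0.6745, where the normal density is 0.3178.
- Mean baseline of those kept: 0.3178 / 0.75 = 0.424.
- Expected fall: (1 − R) × 0.424, which is 0.5 × 0.424 = 0.21, 0.3 × 0.424 = 0.13, and 0.1 × 0.424 = 0.04 SD.
- Baseline variance of those kept: 1 − 0.424 × (0.424 + 0.6745) = 0.535.
- Variance of change: (1 − R)² × 0.535 + R(1 − R) + q(1 − R). Here q is the post error variance relative to baseline: q = 1 if equally noisy, and q = 7/28 = 0.25 if daily errors are independent.
- Example, R = 0.5 and q = 1: 0.134 + 0.25 + 0.5 = 0.884, so SD = 0.940. Noncentrality with 38 per arm is (0.212 / 0.940) × √38 = 1.39, against a critical t of 2.03.

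Simulated rate of a significant fall in the EFT arm (paired t test, two-sided 0.05, favourable direction only; nominal 2.5%):

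| R | Fall (SD) | 38 per arm, q = 1 | 38 per arm, q = 0.25 | 26 per arm, q = 1 | 26 per arm, q = 0.25 |
|---|---|---|---|---|---|
| 0.5 | 0.21 | 27% | 42–43% | 19% | 30–31% |
| 0.7 | 0.13 | 17% | 26% | 13% | 19% |
| 0.9 | 0.04 | 8% | 11% | 7% | 9% |

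EFT versus CET on the same simulated data stays between 2.4% and 2.6%. Counting either comparison as success adds about one point or less to the within-arm rate.

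Sensitivity (38 per arm, q = 1):
- With 80% kept, the rates are 20%, 13% and 7%. Protocol 14.1 expects more than 80% of those consented to be randomized.
- At level 0.01, used in both sizings, they are about 10.5%, 6% and 2%, against a nominal 0.5%.

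**The case against.** **The objective is a summary sentence, not a decision rule.** This stands. It sets no test and no significance level, so a reader who infers a formal criterion that EFT can pass on baseline alone goes beyond the text. Protocol 4.1 asks for both comparisons and does not call the first sufficient; it also says within-subjects, not within the EFT arm. What remains is that nothing stops a baseline-only result from being reported under the primary objective.

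**The operative analysis text points to CET.** Largely true, as set out above. It shows the intended test and makes the correction easy, but it does not remove the looser wording.

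**Regression to the mean does not reach the whole objective.** Correct. The current criteria do not select on the level of discounting, demand or craving. A reader might infer that every primary measure is biased in this way. The documents support that directly only for drinks per day and, by close relation, BrAC. For the other measures, a pre/post change simply has no control.

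**The wish to cut down.** A reader might add that this inclusion criterion lowers drinking after baseline. It already applies during the baseline week, and the documents do not show a further fall. It is not counted here.

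**The rates are assumed.** Also true. The highest figures need independent daily errors, whereas the SAP expects AR(1) dependence between days. The SAP also plans multiplicity correction, which is not modelled.

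**Conclusion.** The point holds as a fault of wording that affects what the trial may conclude. The objective and endpoint text permit an uncontrolled claim, and for drinks per day and BrAC the baseline-week selection tilts that claim towards benefit.

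Under the stated assumptions, with 75% kept and two-sided 0.05, the false-benefit rate ranges from about 7% to 43% across the reliabilities, arm sizes and noise levels tried, against 2.5% for EFT versus CET. It is lower if 80% are kept or the level is 0.01. The top of that range should not be quoted alone: it needs reliability 0.5 and a post measure with a quarter of the baseline error variance.

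The randomised comparison is not biased by the selection, because selection precedes randomization and applies to both arms. No change to design, data collection or sample size follows from this point.

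**What to change.** - **Protocol 1.0, Primary Objective:** delete *baseline and/or*, and state that the baseline-adjusted EFT versus CET contrast is the sole basis for the primary conclusion.
- **Protocol 4.1, and SAP Alcohol Consumption and AUQ:** label within-arm pre/post changes descriptive, with no claim of efficacy.
- **Protocol 5.2 and SAP Objective 1:** name that same contrast as the deciding one, so that a time effect is not read as an EFT effect.

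The cost is wording only. The trial gives up a claim that has no control behind it.

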2.0 Objectives

2.1 *Describe the purpose, specific aims, or objectives of this study:*

Test reinforcer pathology via manipulation of the temporal window in the real world.

2.2 *State the hypotheses to be tested:*

We hypothesize that an intervention involving episodic future thinking (EFT) will increase the temporal window and dynamically decrease alcohol valuation (i.e., consumption of alcohol in the real world, demand, and craving).

3.0 Background

3.1 *Summarize the relevant prior research on this topic and gaps in current knowledge within the field of study:*

Episodic future thinking (EFT) is based on the new science of prospection, which was first identified in a *Science* publication in 2007 and refers to pre-experiencing the future by simulation. Considerable evidence suggests that prospection is important for understanding human cognition, affect, motivation, and action. Individuals with damaged frontal areas, as well as individuals with alcohol use disorder (AUD), show deficits in planning prospectively. One systematic method to engender prospection is via EFT. EFT, as applied in our prior studies and in this proposal consists of having participants develop positive plausible future events that correspond to several future time frames (e.g., 2 weeks, 1 month, 3 months etc.). For each of these timeframes participants are asked to concretize the events (e.g., What are you doing? Who will be there? What will you see, hear, smell, and feel?).

3.2 *Describe any relevant preliminary data:*

We and others have used EFT to decrease delay discounting (DD) in individuals with AUD and smokers, as well as normal weight, overweight, and obese populations when

compared to the control condition, control episodic thinking (CET). Consistent with reinforcer pathology, EFT also reduces alcohol valuation in the purchase task among individuals with AUD and decreases alcohol consumption when EFT cues are texted to participants during a normal day over the course of 2 weeks.

3.3 Based on the existing literature, provide the scientific or scholarly rationale for and significance of your research and how will it add to existing knowledge:

In this study, we propose to test an intervention, EFT, which we hypothesize will decrease reinforcer pathology measures in the real world over a longer time frame than has been done previously; that is, EFT will decrease delay discounting, as well as alcohol consumption in the real world, demand, and craving compared to a control episodic thinking (CET) condition. Moreover, we hypothesize EFT will enhance activation in brain regions associated with prospection (e.g., hippocampus and amygdala) and the executive decision system (e.g., DLPFC). Not only will results from these analyses help demonstrate the mechanisms by which EFT operates, but also contribute to the understanding of EFT as a potential therapeutic behavioral intervention.

